14.2 Biospecimen Collections

14.21 Optional Blood Biospecimens

Two 10-mL EDTA tubes of whole blood are requested for correlative studies and for potential future research should the patient consent to giving a blood sample for research purposes.

14.22 Optional Tissue Biospecimens

Either frozen (preferred) **or** FFPE tissue specimens from **each** surgical site of disease and a sample of the intervening non-malignant tissue will be submitted for tissue correlative science evaluation and potentially for future research, should the patient consent. Tissue from axillary lymph nodes (sentinel lymph nodes and/or axillary lymph node dissection dependent on case) will also be collected for correlative science evaluation (see Table 14.1.) **A corresponding H&E slide for each submitted block must be provided** to permit quality assessment of each tissue block.

If frozen tissue cannot be provided, the FFPE tissue block is requested. However, **if an institution is unable to provide a tissue block**, cut fifteen

5-micron positive charged slides. **Label the slides with patient study ID number, pathology accession number, and order in which the sections were cut from the block.** H&E stain the first and last five micron slide that is cut (i.e., slides labeled 1 and 15). These H&E slides will be reviewed centrally for assessing tissue quality. The remaining unstained slides will be processed as described in section 14.4. For samples containing less than 7 square millimeters of tumor tissue, multiple sections should be mounted onto each slide to ensure that the appropriate amount of tumor tissue is available. Ideally, each slide must have a minimum of 75 % tumor tissue on the slide to be deemed adequate for study. **Do not bake or place covers slips on the slides.**

14.3 Biospecimen Processing and Submission

14.31 Biospecimen Kits

Blood: Blood specimen kits are required.

Tissue: If an institution is capable of collecting and shipping frozen tissue specimens, kits are strongly recommended and will be provided to each institution on request.

Sites may order these kits **in advance** at no charge from the Alliance-Central Specimen Bank by contacting [REDACTED] or by email to [REDACTED] Kits will be sent via FedEx® Ground at no additional cost to the participating institutions. **Allow at least two weeks to receive the kits.** Kits will arrive inside the shipping boxes. Kits will not be sent via rush delivery service unless the requesting site provides their own FedEx® account number or alternate billing number for express service. **Alliance will not cover the cost for rush delivery of kits.**

14.32 Blood Processing and Submission

Ship two 10 mL EDTA tubes with a properly prepared cold pack. See kit instructions for specific details for cold pack preparation (i.e., frozen or refrigerated) and proper packing of blood and cold pack to avoid freezing of specimen.

14.33 Tissue Processing and Submission

14.331 Frozen Tissue Processing and Submission

After breast conservation surgery, the specimens should be brought to the pathology department as soon as possible (generally speaking, this means within 15 minutes after the time of tissue resection). **If possible, in order to accurately record the *ex vivo* ischemia time, the time at which the specimens are excised from the patient should be recorded.** The specimens should be kept fresh and not put into any type of fixative, although it may be transported to pathology in a solution of normal saline or any other physiologic buffer. The specimens should be reviewed by the attending pathologist or other

authorized individual (pathology resident, fellow, or qualified pathologist assistant). Material needed for diagnosis should be removed and processed according to the institution's standard procedures. Any remaining tissue may be sent to the Alliance Central Specimen Bank.

Where possible, representative and grossly apparent tumor tissue from each foci of disease and one sample of intervening normal breast tissue should be collected. Where two foci of disease are resected in one lumpectomy, non-malignant tissue from the area between the two tumors should also be submitted. Where two separate foci of disease are resected in separate lumpectomies, non-malignant tissue from the area between the two tumors is ***not required*** to be submitted. Normal tissue from the margin of the lumpectomy specimen can be submitted as the intervening normal tissue. Tissue that is grossly necrotic, hemorrhagic or cauterized should be avoided. Tissue should be rapidly divided into segments no larger than 1 cm³ (1 gram). As many as possible (but at least one) of these sized segments should be collected from each site of disease.

If the foci are removed separately and margins on both are negative, it is assumed that the radiographic distance (closest distance by MRI or mammogram) would be the appropriate separation.

Place the tissue segments in the tissue cassettes provided (usually 2-3 segments of tissue per cassette). Use multiple cassettes if necessary - do not "stuff" large amounts of tissue into a single cassette. Label the cassette with 'T' for tumor or 'N' for non-malignant tissue using the marker provided. Wrap each cassette in a piece of foil (provided in the kit). Place the cassette at one end of the foil and roll the foil around the cassette. Carefully fold over the ends of the foil and crease them tightly to create a sealed, compact packet. Immediately immerse the foil-wrapped cassette in liquid nitrogen for 5 minutes. If liquid nitrogen is not available, the specimen may be immersed in an isopentane cryobath available in most surgical pathology frozen section rooms. If using a cryobath, be certain that the temperature of the bath is at or below - 40° C. As a last option, specimens may be frozen by complete immersion in an ethanol / dry-ice bath. Specimens should be left in the cryobath or dry ice bath for at least 15 minutes to ensure complete freezing. Specimens should not be frozen by placing fresh tissue in an - 80° C freezer or inside a cryostat. **The time at which the tissue is frozen should be recorded so that, together with the recorded time of operative resection, the *ex vivo* warm ischemia time can be calculated.**

Once frozen, foil-wrapped tissue cassettes should be placed in one or more of the zip-lock bags provided. Be certain that the specimen bag is accurately and legibly labeled with the patient study ID number. **Once frozen, take extreme care not to let the tissue specimen thaw.** If an ultra-cold freezer (i.e., - 80° C or colder) **is not** available, the specimens must be shipped the same day they are collected and

frozen. If an ultra-cold freezer **is** available, specimens may be stored at -80°C or colder until frozen specimens can be appropriately shipped (≤ 30 days after surgery). The specimens must be shipped with sufficient dry ice for up to two days. **Specimens must remain frozen at all times.**

If resources are not available at the site to collect snap frozen surgical tissue, FFPE tissues must be submitted (see next section).

14.332 FFPE Tissue Processing and Submission
 FFPE blocks/slides should be submitted from each of the foci of malignancy and also where available from the intervening non-malignant tissue (as described above). The block/slides must be appropriately packed to prevent damage (i.e., slides should be placed in appropriate slide container) and placed in an individual plastic bag. Tissue specimens must be shipped ≤ 30 days after surgery.

14.34 General Biospecimen Shipping Instructions

Use of the Alliance Biospecimen Management System (BioMS) is mandatory and all specimens must be logged and shipped via this system.

BioMS is a web-based system for logging and tracking all biospecimens collected on Alliance trials. Authorized individuals may access BioMS at the following URL: [REDACTED] using most standard web browsers such as Internet Explorer, Safari and Firefox. For information on using the BioMS system, please refer to the 'Help' links on the BioMS webpage to access the on-line user manual, FAQs and training videos. To report technical problems, such as login issues or application errors, please contact [REDACTED]. For assistance in using the application or questions or problems related to specific specimen logging, please call [REDACTED]

After logging collected specimens in BioMS, the system will create a shipping manifest. This shipping manifest must be printed and placed in the shipment container with the specimens.

All tissue and blood specimens collected for correlative studies are shipped to the Alliance Central Specimen Bank (CSB) where they will be permanently stored unless a specific request is made to return materials for the purpose of individual patient care or if the patient requests that her materials be returned.

Specimens may be shipped Priority Overnight to the Alliance CSB on Monday through Thursday for next day delivery. The Bank cannot receive specimens on Saturdays, Sundays or holidays. **Do not send specimens on Friday, Saturday or the day before a holiday.**

Sites are responsible for the costs of shipments; however, federal funds for the submission of whole blood and FFPE/frozen tissue specimens are included in the payment schedule and paid upon confirmation of receipt of the specimens.

14.4 Biospecimen Use

14.41 Blood Use

DNA will be extracted from EDTA whole blood and white blood cells will be prepared from residual blood. Similar to the tumor samples being collected in this study (see the following section), DNA will be isolated and subjected to 1) gene expression profiling; 2) array comparative hybridization; and 3) gene sequencing for significantly mutated genes. These studies will be performed in conjunction with the tumor studies.

14.42 Tissue Use

When patients present with multifocal disease, it is unclear whether this represents multiple separate primary cancers or the manifestation of one tumor that has disseminated through the breast to create separate nodules but with similar genomic characteristics. This distinction may have important clinical consequences. Two entirely unrelated cancers arising separately in the same breast could quite logically be treated as separate tumors from the surgical standpoint, but from the medical standpoint may need different systemic approaches. In contrast, tumors that appear separate but are in fact genetically similar may represent wide dissemination of the same malignant process and may not be suitable for conservative breast surgery, but would be treated with the same systemic approach.

To begin to explore this question we will apply genomic approaches, including gene expression, gene copy and gene sequencing to the multiple tumor sites to try to differentiate between these two possibilities. Tumors with similar gene expression profiles, copy number aberrations and somatic mutations will be called related; tumors where these features are discordant will be called unrelated. Clearly one can also envisage the possibility of multi-clonality where two separate nodules have a common precursor but have diverged over time. In this setting, the digital nature of next generation sequencing is very valuable, as not only will we be able to compare a list of mutations, but their frequency, allowing us to study clonality in an efficient way.

These experiments will be conducted in two settings. The first setting is in a subset of patients with three available data sources: 1) have consented to whole genome sequencing; 2) a frozen specimen from each tumor acquired by the surgeon or pathologist; and 3) a germ-line specimen (tube of peripheral blood). This will allow a very deep unbiased genomic analysis and will provide the most definitive data on the relatedness of two separate sites of disease in the breast. The second setting is where one of these three data sources is missing. For patients who did not consent for genomic studies or in whom only fixed material is available or the germline DNA is not available we will use techniques adapted to formalin fixed material to examine selected breast cancer genes for mutation or expression to determine relatedness.

Since this type of analysis has not been attempted before, all statistics will be exploratory; however our primary hypothesis is that unrelated tumors that are

fully excised have a low local recurrence upon breast conservation surgery. In contrast, multiple related tumors will have a high rate of local recurrence because functionally tumors are widely disseminated throughout the breast even though the margins of excision appear negative.

DNA and RNA will be isolated from each separate tumor site and subjected to 1) gene expression profiling (addressing the question of whether the tumor foci have the same or different intrinsic subtype (basal-like, luminal A, luminal B, HER2-enriched, claudin-low); 2) array comparative hybridization (to determine whether they have the same or different patterns of gene copy variation, e.g., LOH and amplification) and 3) gene sequencing. The sequencing will be full genome in a subset of patients where high quality frozen samples were taken and are available from each tumor site. Then in all cases, a sequencing assay for significantly mutated genes in breast cancer can be performed on routinely formalin-fixed tumor material.

Formalin fixed surgical pathology blocks requested to accommodate individual patient management will be returned promptly upon request.

14.5 Return of Genetic Testing Research Results

Because the results generated by the genetic testing described above are not currently anticipated to have clinical relevance to the patient or their family members and will be conducted in a research facility, the genetic results will not be disclosed to the patients or their physicians.

If at any time, incidental genetic results are obtained that may have clinical relevance, IRB review and approval will be sought regarding the most appropriate manner of disclosure and whether or not validation in a CLIA-certified setting will be required prior to reporting any finding. Sharing of research data with individual patients should only occur when data have been validated by multiple studies and testing has been done in CLIA-approved laboratories or in a setting where a clinical trial is available based on a CLIA laboratory validated sequencing result and the patient has consented to re-contact for additional studies.

15.0 Whole Breast Irradiation (WBI) Risks

15.1 Risks and Side Effects Related to the Whole Breast Irradiation (WBI)

Risks and side effects related to the WBI include the following:

Likely (*Events that occur more than 10 % of the time*)

- Reddening of the skin during treatment and for several weeks following treatment
- Tanning of the skin lasting months and may be permanent
- Slightly smaller breast size or change in the way the breast looks
- Tiredness and weakness during treatment and for several weeks following treatment
- Muscles in chest wall under treated breast may feel tight or sore
- Swelling of breast

Less Likely (*Events that occur 3 to 9 % of the time*)

- Peeling of the skin in the area treated with radiation
- Pain at the site of radiation treatment

Rare but serious (*Events that occur < 3 % of the time*)

- Cough
- Difficulty breathing
- Irritation of the sac surrounding the heart
- Inflammation of the heart muscle
- Rib fracture
- Another cancer due to radiation therapy

16.0 Statistical Considerations and Methodology**16.1 Overview**

A single arm phase II clinical trial design will be used to assess whether the local recurrence (LR) rate at 5 years in women with multiple ipsilateral breast cancers who undergo breast conserving surgery is greater than 8 %.

16.2 Study Endpoints

The primary endpoint for this trial is the diagnosis of a local recurrence as a first event where a local recurrence is defined as histologic evidence of ductal carcinoma *in situ* or invasive breast cancer in the ipsilateral breast or chest wall.

The cumulative incidence of local recurrences will be estimated in the competing risk framework as described by Marubini and Valsecchi where regional recurrences, distant recurrences and death without a local recurrence will be considered competing risks and contralateral breast and non-breast second primary cancers will not be considered competing risk.

All eligible patients who have undergone breast conservation surgery with 2 or 3 sites of disease resected to negative margins (i.e., not converted to mastectomy or have not refused mastectomy for positive margins) will be included in the analysis of the primary endpoint.

Secondary clinical endpoints are:

- The conversion rate to mastectomy secondary to persistent positive margins; poor cosmesis within the first year of attempting breast conservation surgery (BCS); or inability to satisfy radiation dose constraints on the boost to the lumpectomy bed of each site of disease
- The type and severity of adverse effects of breast conserving surgery and radiation for women with multiple ipsilateral primary breast cancer (MIBC)
- The radiation-related side effects of whole breast radiation with a boost to 1 large or > 1 lumpectomy site
- The patient's perception of cosmesis.

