7.6 Adjuvant Whole Breast Irradiation (WBI)

Patients receiving BCT should receive adjuvant whole breast radiation with a boost to the lumpectomy bed of each site of disease. The boost will be limited to two quadrants of the breast only. **Note:** Patients who cannot or do not receive boost radiation are ineligible and must discontinue the study. The end of study information should be collected and the patient referred to clinical care. Addition of nodal radiation fields will be at the discretion of the treating radiation oncologist.

Patients may receive WBI at an institution other than the enrolling institution. Note that the enrolling institution is responsible for the correct performance of WBI at the other institution and the reporting of all study data. The institution performing WBI must follow all requirements for WBI listed in the protocol, including regulatory requirements such as submission of an RTFI form to CTSU and submission of treatment plans to IROC Rhode Island (QARC).

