7.61 Treatment Planning/Delivery

- 7.611 Three-dimensional CT-based treatment planning is required.
- 7.612 Heterogeneity corrections are required.
- 7.613a Intensity modulated radiotherapy (IMRT) with inverse planning is allowed.
- 7.613b Breath hold technique is allowed
- 7.614 Optimization with forward planning is allowed.
- 7.615 Linear accelerators with minimal photon energies of 6MV and electron energies of 6eMEV-20eMEV are required.
- 7.616 Either electrons or photons may be used for boost treatment.
- 7.617 Boost treatment to each lumpectomy cavity is required.
Note: Patients who cannot or do not receive a boost are ineligible and must discontinue the study. The end of study information should be collected and the patient referred to clinical care.
- 7.618 Boost with intraoperative radiotherapy or HDR brachytherapy is not allowed.
- 7.619 Hypofractionation is not allowed.

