7.65 Target Volumes

The definitions for the CTV, PTV and normal structures used in this protocol generally conform to the RTOG-endorsed consensus guidelines for delineation of target and normal structures for breast cancer

7.651 Breast volumes

7.6511 Breast CTV

Includes the palpable breast tissue demarcated with radio-opaque markers at CT simulation, the apparent CT glandular breast tissue visualized by CT, consensus definitions of anatomical borders, and the Lumpectomy CTV from the breast cancer atlas. The breast CTV is limited anteriorly within 5 mm from the skin and posteriorly to the anterior surface of the pectoralis, serratus anterior muscle excluding chest wall, boney thorax, and lung. In general, the pectoralis and/or serratus anterior muscles are excluded from the breast CTV unless clinically warranted by the patient's pathology. The breast CTV should generally follow consensus guidelines

7.6512 Breast PTV

Breast CTV + 7 mm 3D expansion (exclude heart and do not cross midline).

7.6513 Breast PTV Eval

Since a substantial part of the Breast PTV often extends outside the patient, the Breast PTV is then copied to a Breast PTV Eval which is edited. This breast PTV Eval is limited anteriorly to exclude the part outside the patient and the first 5 mm of tissue under the skin (in order to remove most of the build-up region for the DVH analysis) and posteriorly is limited to no deeper than the anterior surface of the ribs (excludes boney thorax and lung). This Breast PTV Eval is the structure used for DVH constraints and analysis. This Breast PTV Eval cannot be used for beam aperture generation.

7.652 Lumpectomy volume

7.6521 Lumpectomy GTV

Contour using all available clinical and radiographic information including the excision cavity volume, architectural distortion, lumpectomy scar, seroma and/or extent of surgical clips.

Patients without a clearly identifiable lumpectomy bed are not eligible for protocol participation.

7.6522 Lumpectomy CTV

Lumpectomy GTV + 1 cm 3D expansion. Limit the CTV posteriorly at anterior surface of the pectoralis major and anterolaterally 5 mm from skin and should not cross midline. In general, the pectoralis and/or serratus anterior muscles are excluded from the lumpectomy CTV unless clinically warranted by the patient's pathology.

7.6523 Lumpectomy PTV

Lumpectomy CTV + 3-5 mm 3D expansion (excludes heart).

7.6524 Lumpectomy PTV Eval

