13.3 Discontinuation After Surgery but Prior to Completion of WBI

Patients who discontinue the study after surgery but prior to completion of WBI due to any of the following:

- patient refusal to undergo or complete WBI;
- physician discretion;
- unacceptable toxicity preventing administration/completion of WBI

will go to the observation phase of this trial; that is, they be followed as per the test schedule for 5 years after treatment discontinuation.

Note: Patients who cannot or do not receive boost radiation are ineligible and must discontinue the study. The end of study information should be collected and the patient referred to clinical care.

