13.5 Definition of Ineligible

A patient is deemed *ineligible* by the data center if, after registration, it is determined that at the time of registration, the patient did not satisfy each and every eligibility criteria for

study entry.

- If the patient did undergo surgery with/without radiation, submit all treatment/intervention forms and the Off Treatment/Cancel Notification Form.
- If the patient did not undergo surgery, submit on-study material and the Off Treatment/Cancel Notification Form. No further data submission is necessary.

Note: If, after a site has registered a patient into the study, the site becomes aware of information that questions the patient's eligibility for the study, the site should contact the QAS/Data Manager at the telephone number and/or email address listed on the Protocol Resources page of the protocol.

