16.6 Analysis Plan

16.61 Local Recurrence Rate

All eligible patients who have undergone surgery that was not converted to a mastectomy and who did not have a finding of single contiguous area of malignancy on final pathology will be included in the analysis of the primary endpoint.

The cumulative incidence of local recurrences will be estimated in the competing risk framework as described by Marubini and Valsecchi where regional recurrences, distant recurrences and death without a local recurrence will be considered competing risks and contralateral breast and non-breast second primary cancers will not be considered competing risk. A 95 % Poisson confidence interval for the cumulative incidence of a local recurrence within 5 years will be constructed.

Gentilini *et al.* reported that cumulative incidence of local recurrence differed in terms of estrogen receptor status, HER2/neu expression, Nottingham grade, and Ki-67 expression (univariately) (Gentilini *et al.*, 2009). Gray's test will be used to explore whether the cumulative incidence of local recurrence differs with respect to these factors as well as progesterone receptor status, number of positive lymph nodes, number of foci, t-stage, age, perception of quality of life as measured by LASA at registration (poor: 0 to 3; middling: 4 to 7; good/excellent: 8 to 10), and fatigue as measured by LASA at registration (none to little: 0 to 3; some: 4 to 7; a great deal: 8 to 10).

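### The primary set is limited to eligible patients, but the documents do not settle whether women without a boost are eligible or whether their local recurrences are collected

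*Combined protocol and SAP*

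**What the plan says.** The primary set is defined twice. Section 16.2 takes "All eligible patients who have undergone breast conservation surgery with 2 or 3 sites of disease resected to negative margins". Section 16.61 takes "All eligible patients who have undergone surgery that was not converted to a mastectomy and who did not have a finding" of one contiguous malignancy. Neither refers to whole breast irradiation (WBI) or to the boost.

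The word *eligible* is used in two ways:

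- Section 13.5 calls a patient ineligible if "at the time of registration, the patient did not satisfy each and every eligibility criteria for" study entry. Section 3 contains no criterion on receiving a boost.
- The note in 7.6 reads "Patients who cannot or do not receive boost radiation are ineligible and must discontinue the study", followed by "The end of study information should be collected and the patient referred to clinical care". Section 7.617 has a near-identical note ("Patients who cannot or do not receive a boost are ineligible and must discontinue the study"), and the 7.6 note is repeated in 13.3.
- Section 7.6521 adds "Patients without a clearly identifiable lumpectomy bed are not eligible for protocol participation". This is a finding at radiation planning, which comes after registration for anyone registered before surgery.

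On follow-up, the list in 13.3 covers "patient refusal to undergo or complete WBI", physician discretion and unacceptable toxicity. It sends these women to observation for 5 years on the test schedule. Footnote 1 to the study phases in 18.2 also sends refusals, adverse events and physician-discretion cases to observation, with no exception for a missing boost. Section 13.2 ends participation and data submission for women who do not meet the dose constraint, while women converted to mastectomy within a year are followed yearly for survival.

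**The concern.** A woman who has had breast conservation with negative margins and then receives no boost met every entry criterion, so under 13.5 she is eligible. Under the notes she is not. The analyst preparing the primary set has no text that decides between the two.

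The data problem is more serious than the label. If a site follows the note, it stops collecting local recurrences (LR) from that woman because of treatment received after registration. If it follows the 13.3 list, it delivers 5 years of data on the same kind of patient. Recurrences that were never collected cannot be recovered at analysis, whichever definition is then chosen.

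The stated target does not help. Section 16.1 asks about women who undergo breast conserving surgery; 1.2.1 speaks of surgery and radiation therapy. Women without a boost may belong to the first group and not to the second.

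**Working it through.** **Step 1. The passages side by side.**

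| Woman | 13.3 list, 18.2 footnote 1 | No-boost note | 13.2 | Eligible? |
|---|---|---|---|---|
| Stops before the boost: refusal, physician discretion, toxicity | Observation; 5 years on the test schedule (13.3) | Off study, end-of-study information only | Not named | Yes by 13.5, no by the note |
| Dose constraint not met, no mastectomy | Not named | Off study, end-of-study information only | Terminated, no further data | Yes by 13.5, no by the note |
| Mastectomy within a year | Not named | Not needed | Observation; yearly survival | Excluded by 16.2 and 16.61 in any case |

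Only the first row has contradictory follow-up rules. The second has a clear data rule, but the same doubt about eligibility.

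**Step 2. Can the note be an exception to the 13.3 list?** A woman who refuses WBI or never starts it receives no boost. If the boost follows the whole-breast fractions, a woman who stops during those fractions receives none either. The exception would leave the list only women whose boost was begun and not finished. It would also leave footnote 1 of 18.2 unexplained.

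**Step 3. Reproduce the decision rule in 16.3.** Inputs: 200 eligible patients, Poisson counts, 95% interval, threshold 8%. The exact two-sided upper limit for k events is U(k) = χ²(0.975; 2(k+1) df)/2, divided by N.

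- U(8) = 15.7632; 15.7632/200 = 7.88%, below 8%.
- U(9) = 17.0848; 17.0848/200 = 8.54%, above 8%.

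So 8 is the maximum, as 16.3 states. Section 16.61 gives no formula; the exact two-sided form is my assumption, and it reproduces the rule. A one-sided 95% limit or a Wald limit would allow 9 events (7.85% and 7.44%).

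**Step 4. Boundary illustration with one woman without a boost (assumed counts).**

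- She has an LR and it is counted: 9/200, upper limit 8.54%. Nine also exceeds the limit of 8 in 16.51.
- She has an LR and it is not counted: 15.7632/199 = 7.92%.
- She has no LR and is followed: 8/200, 7.88%. Dropped: 8/199, 7.92%.

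The effect can therefore go either way.

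**Step 5. Does keeping her in the set without follow-up help?** Take 200 women, m of them censored at about 10 weeks, 8 LR among the others from 0.5 years on, no competing events and otherwise complete follow-up. The 5-year cumulative incidence is 8/(200 − m), and scaling by U(8)/8 gives 15.7632/(200 − m). For m = 1: 8/199 = 4.02% and 7.92%. For m = 10: 8/190 = 4.21% and 8.30%. These equal the results of dropping the same women, so relabelling them as eligible does not replace their data.

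**The case against.** Three arguments on the other side carry weight.

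*Replacement.* A reader might infer that the trial can lose only two women, since 15.7632/0.08 = 197.04, so that 8/198 gives 7.96% while 8/197 gives 8.002%. The documents do not support that. Section 16.3 enrols 265 to obtain 200 evaluable, and its allowance includes women found ineligible after consent, where no-boost women might be placed. The final number is not fixed at 200 minus the losses, and the crossing at 197 is by 0.002 percentage points. What remains is that replacement restores numbers but does not undo selection on later treatment. Nor do the 65 extra patients (265 − 200) give a count, because 16.3 does not name a missing boost.

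*A workable reading.* Section 13.5 is the only headed definition of ineligible and is applied by the data center. The notes can be read as off-study instructions, and 7.6521 speaks of protocol participation, not analysis. A reader might infer that the note removes women from the primary set; that is one reading, not a settled fact. The milder reading does not restore follow-up data, however.

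*A defensible target.* Both definitions already condition on events after registration for women registered before surgery: no mastectomy in both, negative margins in 16.2. Given 1.2.1, confining the question to women who received the studied treatment would be legitimate. Conditioning of this kind is not an error in itself; the fault is that the choice is not stated.

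The other differences between 16.2 and 16.61 are minor. The reference in 16.2 to two or three sites arguably excludes a contiguous lesion already, and women with persistent positive margins either convert or are terminated under 13.2.

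**Conclusion.** The concern holds and should be fixed. The documents do not say whether women without a boost belong to the primary set. For those who stop before the boost through refusal, physician discretion or toxicity, they give contradictory follow-up rules. Under the note, such women are either dropped or censored early because of treatment received after registration.

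The documents give neither the number of these women nor their recurrence rate, so the size and direction of any bias are unknown. The 8.54% against 7.92% contrast shows only that one recurrence can matter near the limit; it assumes about 200 evaluable women, 8 or 9 events and an exact two-sided Poisson limit. It does not predict that the result will change. The arithmetic in 16.3 is correct.

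**What to change.** 1. Put one identical primary-set definition in 16.2 and 16.61. Judge eligibility at registration as in 13.5, and add the post-surgical conditions the plan already intends: breast conservation with negative margins, no conversion to mastectomy, no single contiguous malignancy. State explicitly whether women without a boost are included.
2. Reconcile 7.6, 7.617, 7.6521 and the note in 13.3 with 13.5, the list in 13.3 and footnote 1 of 18.2. This concerns analysis eligibility and data collection only; no clinical rule on the boost or on stopping treatment needs to change.
3. Where consent allows, collect yearly local-recurrence status for women who stop without a boost and do not convert to mastectomy, including those who fail the dose constraint. The event-monitoring phase in 13.4 and its forms in 18.2 already collect yearly disease status. For the dose-constraint group this adds to the data rule in 13.2, which would need matching wording.
4. Report the 5-year cumulative incidence of local recurrence with and without these women, which covers the target as worded in both 16.1 and 1.2.1.

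The cost is edits to these sections, a few yearly forms and one sensitivity analysis. The estimate may move in either direction. Section 16.3 shows that this version was written during the study, so some women may already be off study, and their data may not be recoverable.
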